Empower Opioid Misuse & Chronic Pain (RAP_EOM)

NCT04184362

5/1/2023

Contents:

- Study Protocol
- Statistical analysis plan

Study Protocol

This pilot study aims to examine the feasibility, acceptability, and preliminarily examine efficacy of transcutaneous electrical nerve stimulation (TENS) at the ulnar nerve, in reducing opioid craving and use and decreasing pain. Opioid prescribing for chronic pain has increased dramatically over the past several decades, with devastating public health consequences, including high rates of opioid misuse and overdose deaths. Safe nonpharmacological treatments are urgently needed. Preclinical studies have shown that peripheral nerve stimulation at the ulnar nerve (ulnar aspect of the palm) through acupuncture or electrical stimulation directly regulates the mesolimbic dopaminergic pathway and reduces addictive behaviors. In addition, neurostimulation at acupressure points may reduce some types of chronic pain. Empower (TheraNova, LLC) is a non-invasive, portable TENS device that provides electrical stimulation at the ulnar nerve, which may reduce cravings and improve pain. We propose a single-blind, randomized controlled trial to examine the feasibility and to preliminarily examine efficacy of Empower in reducing opioid craving and opioid use in Veterans with chronic non-cancer pain (NCP). Aims are to examine the feasibility and acceptability of Empower and preliminarily examine its efficacy in reducing cravings, decreasing opioid use, and reducing pain when used at the ulnar nerve. Up to thirty veterans with chronic NCP and opioid misuse will be recruited. On Days 1- 7, participants will undergo baseline monitoring, and on Days 8-21, participants will undergo daily neurostimulation at ulnar nerve (n=15) or a control acupoint on the dorsal bicep (n=15). Study procedures will occur at home over 3 weeks, through secure two-way video or phone conference, with outcome assessments occurring at Days 0, 7, and 21. Pain scores, craving, and opioid use will be measured daily Days 0-21. Our goal is to provide an intervention that, alone or in conjunction with current treatments, reduces craving and reduces reliance on opioids in high-risk chronic pain patients.

PROCEDURE

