visit. To encourage self-monitoring during treatment sessions, participants may optionally self-monitor heart rate variability, through their own at-home heart rate monitors or through provision of commercialized heart rate monitoring apps. Interested participants will be informed that they may optionally monitor heart rate before, during, or after treatment sessions at Days 0, 7, 14, and 21, from home. Readings will be collected via encrypted message, de-identified and stored in the password protected database.

A urine pregnancy test in women ages 18-50 who do not confirm a reliable method of birth control at screening will also be completed at screening (Day 0), either in the VA lab or at home. The results of at home urine pregnancy test can be shared securely via encrypted email through a photo image of the home test. We will obtain informed verbal consent to communicate with each participant's medical provider to confirm eligibility after verbal consent. Participants who meet all inclusion criteria and none of the exclusion criteria will be enrolled in the study.

The first week (Days 0-7) will be the Baseline Monitoring Phase, in which baseline measures of craving, and pain are completed daily (see below). On Day 7, participants will be randomized to use the Empower device at the ulnar nerve (Treatment Group, n=15) or at the bicep (Sham Group, n=15). The subsequent two weeks will be the Treatment Phase, followed by the Post-Treatment Completion visit at the end of the two- week Treatment Phase. Throughout the study, the participant will complete daily surveys on the Empower app on the provided smartphone and weekly Qualtrics-based questionnaires. The participant will be asked to complete surveys as close as possible to awakening. During the Treatment Phase only, the participant will self-administer a 30-minute treatment two times daily. The participant will be asked to administer treatments approximately 12 hours apart, if possible. The smartphone will have daily notifications to remind the participant to complete surveys and treatments.

The study will include three clinic visits:

- 1) Enrollment and start of Baseline Phase (Day 0),
- 2) Completion of the Baseline Phase and start of the Treatment Phase (Day 7, \pm 5 days to account for scheduling/ weekends), and
- 3) Study Completion (14 \pm 5 days after Visit 2).

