At Baseline (Day 0), the participant will be given the smartphone with Empower app and trained on smartphone and app use. The participant will then be sent home with the smartphone and instructions for use. They will record craving levels and pain levels daily on the Empower app. On Day 7, the study team will use a secure two-way video or telephone conference app to randomize participants into one of two groups (treatment condition (palm) or control condition (dorsal bicep) in a 1:1 ratio according to a computer-generated code provided by the study biostatistician using randomization software. Participants will be randomized in blocks of random size ranging between 4 and 6 to ensure equal numbers in each group and to maintain relative balance between groups as the study progresses. After enrolling a participant into the study, all study materials and devices will be securely delivered to the participant. When the receipt of the materials is confirmed with the participant, study staff will coordinate a tutorial on how to use the device using secure two-way video or telephone conferencing. Once participants demonstrate an understanding for how to use the Empower Neuromodulation System at their designated site, they will then undergo their first self-administered electrostimulation session under study staff supervision.

Starting on Day 8, all participants will self-administer neurostimulation via Empower upon awakening (immediately following completion of the Empower App self-reports) and again approximately 12 hours later. Treatment Condition: Participants will complete a 15-min electrical stimulation application via

Empower on one palm (ulnar nerve acupoint) followed by an additional 15-min stimulation on the opposite palm (30 min per session, 60 min per day). Control Condition: Empower will deliver equal electrical current to the dorsal aspect of the bicep for equal time duration as the Treatment condition.

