Aims 2-3 and Exploratory Aims: Outcome measures will be examined with a series of parallel statistical models, estimated via maximum likelihood, using planned contrasts between the Empower active ulnar nerve treatment condition, the control condition, and the baseline monitoring period. Analyses of in-clinic assessments will compare outcome measures at Days 0, 7, 14, and 21. Given the limited number of assessment points, the most parsimonious model will be a general linear model for each outcome measure. For the daily measures, we will use multilevel modeling to compare changes in variables over days between the treatment and control condition/baseline monitoring period. Analyses will be performed with SPSS.

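### The SAP does not say how baseline enters the active-versus-control contrast, so precision may be lost in the in-clinic models and the handling of chance imbalance at 15 per arm is undefined

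*Combined protocol and SAP*

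**What the plan says.** The efficacy analysis is one paragraph of the Statistical Analysis Plan, headed Aims 2-3 and Exploratory Aims. Models are fitted by maximum likelihood, "using planned contrasts between the Empower active ulnar nerve treatment condition, the control condition, and the baseline monitoring period". In-clinic measures are compared at Days 0, 7, 14 and 21 with a general linear model per outcome. Daily measures get a multilevel model that compares changes over days between the treatment arm and the control condition or baseline period. No model terms or covariates are listed, and no contrast is identified as the between-arm treatment effect.

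The baseline data precede randomisation. The PROCEDURE section states: "The first week (Days 0-7) will be the Baseline Monitoring Phase, in which baseline measures of craving, and pain are completed daily". It then states: "On Day 7, participants will be randomized to use the Empower device at the ulnar nerve", with the bicep as the alternative site. The Study Protocol overview adds: "Pain scores, craving, and opioid use will be measured daily Days 0-21".

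On allocation, PROCEDURE states: "Participants will be randomized in blocks of random size ranging between 4 and 6 to ensure equal numbers in each group". Blocking of this kind balances numbers. No stratification by baseline craving or pain is stated.

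**The concern.** With 15 participants per arm, the arms can easily start at different levels of craving or pain. A participant's own baseline usually predicts later scores, so conditioning on it removes most of such a difference and reduces the variance of the treatment comparison. The trial plans to collect what is needed, but the SAP does not say that the active-versus-control difference will be conditioned on it.

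The paragraph permits several estimators: follow-up values alone, difference in change, or a model in which both arms share one pre-randomisation mean. They differ in precision and in how far a chance imbalance carries into the result. Because the SAP does not choose, the choice could be made after the data are seen. Craving, opioid use and pain are named as primary outcomes, and the SAP says the description of the data is meant to inform later studies. A noisy or imbalance-driven estimate would be a poor basis for planning them.

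**Working it through.** **Inputs from the documents.** Up to 30 participants, 15 per arm, allocated 1:1; about 7 baseline days and 14 treatment days of daily data; randomisation on Day 7. The documents give no power calculation, effect size, SD, alpha or correlation, so there is no figure of the plan's to reproduce.

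**Assumptions.** Equal variances, no dropout, two-sided 5%, 80% power for illustration. Visit-to-visit correlation ρ from 0.3 to 0.7; day-to-day correlation from 0.3 to 0.8, equal between all days.

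**Step 1: chance imbalance.** The baseline difference between arms, in SD units, has standard deviation √(2/15) = 0.365.
- P(over 0.3 SD) = 2 × (1 − Φ(0.3/0.365)) = 0.41.
- P(over 0.5 SD) = 2 × (1 − Φ(0.5/0.365)) = 0.17.
- Median absolute imbalance = 0.674 × 0.365 = 0.25 SD.

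**Step 2: one in-clinic visit, one baseline.** Relative variances of the between-arm contrast are 1 for follow-up only, 2(1 − ρ) for change and 1 − ρ² for analysis of covariance (ANCOVA). Change relative to ANCOVA is therefore 2/(1 + ρ). The difference detectable at 80% power is (1.960 + 0.842) × √(2/15) = 1.02 SD for follow-up only, multiplied by the square root of the relative variance for the others.

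| ρ | Change ÷ ANCOVA variance | Detectable: follow-up only | Change | ANCOVA |
|---|---|---|---|---|
| 0.3 | 1.54 | 1.02 | 1.21 | 0.98 |
| 0.5 | 1.33 | 1.02 | 1.02 | 0.89 |
| 0.7 | 1.18 | 1.02 | 0.79 | 0.73 |

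Estimating the covariate slope costs a factor of about 1 + 1/26 = 1.04 in variance. The ratios then become 1.54/1.04 = 1.48 and 1.18/1.04 = 1.13 at the two ends.

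Given a baseline imbalance, a change contrast carries (1 − ρ) of it, with reversed sign, into the estimate. At the median imbalance of 0.25 SD that is 0.17 SD at ρ = 0.3 and 0.07 SD at ρ = 0.7.

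**Step 3: daily measures, means of 7 and 14 days.** With day-to-day correlation r, the baseline-mean variance is (1 + 6r)/7, the treatment-mean variance is (1 + 13r)/14, and their covariance is r. At r = 0.4 these are 0.486, 0.443 and 0.4.
- Change: 0.486 + 0.443 − 0.8 = 0.129.
- ANCOVA: 0.443 − 0.16/0.486 = 0.113.
- Change ÷ ANCOVA = 1.13; follow-up only ÷ ANCOVA = 3.9.

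Over r = 0.3 to 0.8, change ÷ ANCOVA falls from 1.20 to 1.02, and follow-up only ÷ ANCOVA rises from 2.8 to 19.

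**Step 4: simulation of the readings of the daily model.** 400 trials, 15 per arm, random intercept. Entries are the variance of the estimate, with the share of the baseline imbalance carried into it in brackets.

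| Estimator | r = 0.4 | r = 0.6 |
|---|---|---|
| Follow-up only | 0.0550 (0.79) | 0.0833 (0.93) |
| Group by phase (change), ML | 0.0165 (−0.21) | 0.0110 (−0.07) |
| Three conditions, shared baseline, ML | 0.0140 (−0.02) | 0.0107 (0.02) |
| ANCOVA on baseline-week mean | 0.0145 (−0.03) | 0.0111 (0.03) |

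At r = 0.4 the permitted readings differ almost fourfold in variance (0.0550/0.0140 = 3.9).

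**The case against.** A reader might infer that the plan excludes baseline adjustment, throws the baseline week away and so leaves imbalance uncorrected throughout. The documents do not support that. The SAP lists no covariates but rules none out, and a general linear model can contain one. The baseline data are in the models: as a contrasted condition, as Days 0 and 7, and through the daily analysis of change. If the three conditions are read literally, with one pooled baseline, maximum likelihood matches ANCOVA in Step 4. A group-by-phase reading comes close. This part of the objection stands, and it confines any clear loss to the in-clinic models.

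The follow-up-only figures need an analysis that ignores Days 0 to 7, which is not what the paragraph describes. They mark the edge of what is left open. Nor is 0.37 SD a typical imbalance: it is the standard deviation of the imbalance, and the median is about 0.25 SD.

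The stakes are also modest. This is a proof-of-concept pilot with no power claim. Randomisation keeps the contrast unbiased over repeated trials, so the carry-over matters only given the imbalance that occurs. Craving, pain and opioid use are stated to be measured daily, so the in-clinic loss may fall mainly on other measures.

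What the objection does not remove is that the efficient daily reading depends on a common baseline mean that the SAP never states. That reading also does not settle the in-clinic models.

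**Conclusion.** The point holds as a gap in specification with a probable loss of precision in the in-clinic models. If those models yield a change-type contrast, its variance is 1.54 to 1.18 times that of ANCOVA at assumed correlations of 0.3 to 0.7 (about 1.48 to 1.13 after the small-sample cost). For the daily measures the penalty is at most about 20% under a change reading and nil under a shared baseline. It is large only if follow-up alone is compared.

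Chance imbalance is a real prospect at this size: about 41% beyond 0.3 SD and 17% beyond 0.5 SD for any one measure. These two figures rest only on 15 per arm and a normal approximation. The variance ratios rest on assumed correlations and equal variances. The change is worth making because it costs little, but the point does not invalidate the pilot.

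**What to change.** Add to the Aims 2-3 paragraph of the Statistical Analysis Plan wording to this effect:

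> The treatment effect is the active-minus-control difference. For in-clinic measures it is estimated from post-randomisation values, adjusted for the participant's own pre-treatment baseline (mean of Days 0 and 7). For daily measures it is estimated either with the baseline-week mean of the same measure as a covariate or from a mixed model with a baseline mean common to both arms. The adjusted difference is reported with its 95% CI. Contrasts with the baseline period are reported separately as within-participant descriptions.

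Name one of the two daily options before the data are seen. The second keeps the baseline days as outcomes, so it sits within the existing plan.

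Two details need confirming. The Day 7 value must be recorded before randomisation and before the first supervised session. Daily opioid use in the baseline week appears in the overview, but PROCEDURE lists only craving and pain for that week, so the baseline for opioid use should be stated.

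The cost is SAP wording and about one degree of freedom per model. For craving and pain, the baseline data are already planned for collection.
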